**1.3 Benefit/risk and ethical assessment**

Participants with type 2 diabetes will be randomly allocated to continue with standard care or to receive a 12-week course of intensive lifestyle and glucose-lowering drug therapy which includes Forxiga. All participants will be informed that: a) the trial is testing a new short-term therapeutic approach to treating type 2 diabetes which could eliminate the need for glucose-lowering drugs and possibly promote remission; and b) all therapies will be used for their approved indications. All participants will also provide written informed consent.

**2. STUDY OBJECTIVES**

**2.1 Primary objective**

To determine whether the 12-week metabolic intervention that includes Forxiga is more effective in achieving drug-free remission of type 2 diabetes than standard diabetes therapy when evaluated at 24 weeks after randomization.

**2.2 Secondary objectives**

To determine whether the 12-week metabolic intervention that includes Forxiga is more effective than standard diabetes therapy in achieving diabetes remission and regression when evaluated at 36, 48 and 64 weeks after randomization.

## **2.3 Safety objective**

To determine rates of severe and non-severe hypoglycemic episodes in the treatment groups during 64 weeks of follow-up.

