**Secondary research questions:**

- 1) Compared to the control group, does this therapeutic approach achieve drug-free diabetes remission in a higher proportion of patients than standard diabetes therapy at 36, 48 and 64 weeks after randomization?
- 2) Compared to the control group, does this therapeutic approach achieve drug-free HbA1C <6.0% in a higher proportion of patients than standard diabetes therapy at 24, 36, 48 and 64 weeks after randomization?
- 3) Compared to the control group, does this therapeutic approach achieve drug-free diabetes regression in a higher proportion of patients than standard diabetes therapy at 24, 36, 48 and 64 weeks after randomization? Diabetes regression is defined as HbA1C 6.5-6.9% off glucose-lowering agents for at least 12 weeks.
- 4) What HbA1C levels are achieved in the intervention group and the control group at 12, 24, 36, 48 and 64 weeks after randomization?
- 5) What rates of hypoglycemia are observed in the intervention group and the control group during 64 weeks of follow-up?
- 6) What is the change in weight, body mass index (BMI), waist circumference and waist/hip ratio from baseline to 12, 24, 36, 48 and 64 weeks in the intervention group and the control group?
- 7) Are age, gender, ethnicity, diabetes duration, smoking, family history of diabetes, baseline BMI, waist circumference, HbA1C or fasting plasma glucose (FPG) determinants of diabetes remission at 24 weeks after randomization?

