### **5.3 Interventions and monitoring**

#### **5.3.1 Intensive metabolic intervention (induction phase of the trial)**

An intensive metabolic intervention will be used in intervention group participants for induction of a normoglycemic state. It will be 12 weeks in duration and will include intensive lifestyle therapy and intensive treatment with Forxiga, metformin and insulin glargine. Participants will be asked to discontinue all other glucose-lowering medications.

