#### **5.3.2 Control group follow-up during the induction phase of the trial**

Participants assigned to the standard diabetes therapy group will meet with research personnel at the beginning of the trial who will review self-monitoring of capillary blood glucose, management of hypoglycemia, and the importance of healthy diet and regular exercise in diabetes management. Control group participants will also be provided with a pedometer as an incentive to be active. Glucose levels in standard group participants will be managed by their regular diabetes care provider according to the current Canadian Diabetes Association (CDA) Clinical Practice guidelines. Any approved glucose-lowering medication will be allowed in the control group.

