#### **5.3.3 Monitoring for hyperglycemia relapse during the maintenance phase of the trial**

In all participants, HbA1C will be drawn during week 12 of the trial. At the end of week 12, glucose-lowering medications will be discontinued in all participants with a HbA1C <7.3%, and insulin will be tapered over a 5-day period. Participants will be encouraged to continue with lifestyle modifications and regular home glucose monitoring (i.e. at least 5 fasting capillary measures per week). They will meet with research staff every 2-4 months during the maintenance phase of the trial to review any challenges in achieving and maintaining exercise and weight loss goals. Participants will be assessed by research staff every 1-2 months by telephone to review adherence to lifestyle therapy, SMBG readings and to screen for symptoms of hyperglycemia.

It is possible that glucose levels may quickly rise after glucose-lowering drugs are stopped in some of the participants whose HbA1C is <7.3% on these drugs. This rise may not be detected with HbA1C levels due to the well-known time-lag between rising glucose levels and rising HbA1C levels.

In light of the above, hyperglycemia relapse will be defined as follows:

- a. a HbA1C  $\geq$  7.0% at 24, 36, 48 and 64 weeks; or
- b. reinitiation of glucose-lowering drugs; or

- c. capillary glucose values  $\geq 10$  mmol/L on  $\geq 50\%$  of SMBG readings over 1 week in the absence of an acute illness.

All participants identified to have hyperglycemia relapse will receive standard glycemic management according to the judgment of their physician or investigator. Participants found to have HbA1C  $\geq 7.3\%$  on therapy during week 12 of the trial will also receive standard glycemic management. These participants will continue to be contacted by telephone every 1-2 months to review SMBG readings, medication adherence and side effects.

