### **6.3.5 Period of observation**

For the purposes of this study, the period of observation for collection of adverse events, SAEs, overdoses and any pregnancies extends from the time the participant gives informed consent until the end of the study.

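### Hypoglycemia rates are specified only over 64 weeks, although the tested drug course lasts 12 weeks; rates by phase should be prespecified beside the 64-week rate

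*Combined protocol and SAP*

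**What the plan says.** Two places set the window for hypoglycemia, and both set it at 64 weeks. Section 2.3 states the aim as "To determine rates of severe and non-severe hypoglycemic episodes in the treatment groups during 64 weeks of follow-up". Secondary question 5 in section 1.2 asks "What rates of hypoglycemia are observed in the intervention group and the control group during 64 weeks of follow-up".

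The treatment under test is much shorter. Section 5.3.1 says of the intensive intervention: "It will be 12 weeks in duration and will include intensive lifestyle therapy and intensive treatment with Forxiga, metformin and insulin glargine". Section 5.3.3 then says that "glucose-lowering medications will be discontinued in all participants with a HbA1C <7.3%, and insulin will be tapered over a 5-day period". This stop is not limited to the intervention group: Appendix A Table 1 marks it at week 12 for both groups. Participants at or above 7.3% at week 12, and those who relapse later, go to standard glycemic management. For controls during induction, section 5.3.2 says: "Any approved glucose-lowering medication will be allowed in the control group".

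Section 6.3.1 lists 13 safety outcomes to be collected during the trial. Section 6.3.5 says that the adverse event observation period "extends from the time the participant gives informed consent until the end of the study". Both sections concern collection.

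Section 11.2 offers a chi-squared test for dichotomous secondary outcomes and a t-test or non-parametric equivalent for continuous ones. It gives no method for event rates, no person-time denominator and no safety analysis by phase, although the protocol itself divides the trial into induction and maintenance phases.

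**The concern.** A reader of the results will want to know what a 12-week course of titrated glargine, metformin and Forxiga does to hypoglycemia while it is being given. The only rate that the plan specifies answers a different question. It averages that period with 52 weeks after the course has ended, when an unknown share of each group is off drugs and the rest is on standard management. An excess confined to induction would appear as a much smaller excess per person-year.

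The later period can also pull the comparison in a direction unrelated to the risk of the course. Relapse leads back to drug treatment, and section 11.1 sizes the trial to detect at least 20 points more remission than the 10% expected in controls. If the intervention works, controls may spend more time on drugs after week 12. Separating the phases only after seeing the data, in an open-label trial, would look like a post hoc choice.

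**Working it through.** The documents give no expected hypoglycemia rate, so there is no figure of the plan's own to reproduce. All event rates below are assumed.

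**Inputs**
- Follow-up 64 weeks (2.3, question 5); course 12 weeks (5.3.1); remainder 64 − 12 = 52 weeks, and 52/64 = 81%.
- Insulin taper 5 days (5.3.3): 12 + 5/7 = 12.71 weeks of exposure if it is counted.
- 76 per group (11.1), with no losses assumed: 76 × 12/52 = 17.5 person-years per arm in weeks 0-12, and 76 × 64/52 = 93.5 over 64 weeks.

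**Step 1: 64-week rate in one arm.** With rate r1 in weeks 0-12 and r2 afterwards, the rate is (12 × r1 + 52 × r2)/64.

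**Step 2: excess rate.** If r2 is the same in both arms, the later weeks cancel. The 64-week excess is then 12/64 of the induction excess: 64/12 = 5.33 times smaller, or 64/12.71 = 5.03 times smaller if the excess lasts through the taper. The excess number of events does not change.

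**Step 3: rate ratio.** Let k be the ratio in weeks 0-12.
- No events after week 12 in either arm: the 64-week ratio is still k.
- Same constant background in both arms: the ratio is 1 + (k − 1) × 12/64. For k = 2, 3 and 5 this gives 1.19, 1.38 and 1.75, attenuated but always above 1.
- Constant control rate, with a 64-week ratio of exactly 1: the ratio after week 12 must be (64 − 12k)/52, which is 0.77, 0.54 and 0.08 for k = 2, 3 and 5. This is offsetting by fewer later events, not dilution.

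**Step 4: how far the result depends on controls after week 12.** Assume the intervention arm has 1.0 per person-year in weeks 0-12 and 0.1 afterwards, and control has 0.3 in weeks 0-12 (k = 3.3). The intervention 64-week rate is (1.0 × 12 + 0.1 × 52)/64 = 0.269.

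| Control rate after week 12 | Control 64-week rate | 64-week ratio |
|---|---|---|
| 0.3 | (3.6 + 15.6)/64 = 0.300 | 0.90 |
| 0.2 | (3.6 + 10.4)/64 = 0.219 | 1.23 |
| 0.1 | (3.6 + 5.2)/64 = 0.1375 | 1.95 |

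**Step 5: detectability.** Use z = ln(E1/E0)/√(1/E1 + 1/E0) with Poisson counts, k = 3 and an equal background in both arms.
- Background 0.5 per person-year: 26.3 v 8.8 events in weeks 0-12 (z = 2.82); 64.3 v 46.8 over 64 weeks (z = 1.66).
- Background 2 per person-year: z falls from 5.63 to 3.31 and stays above 1.96.
- Background 0.1 per person-year: z is 1.26 and 0.74, so neither window would show the excess.

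Loss of a signal is therefore possible without any offsetting, but it depends on the assumed rate.

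**The case against.** The strongest reply is that the trial compares strategies under intention to treat: a short course followed by drug cessation, against standard therapy. Fewer events off drugs would be part of what the strategy achieves, so total burden over 64 weeks is a legitimate measure. This stands. The 64-week rate should be kept and not demoted.

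A reader might infer that the plan commits to one pooled rate. It does not. It names a follow-up window, says nothing about a split, and does not rule one out. What remains is that 64 weeks is the only window named.

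A reader might also extend the point to every outcome in section 6.3.1. The documents do not support that. Those outcomes have a collection period but no stated rate, and collecting them to the end of the study is right. Cancers, fractures and deaths may reasonably be followed well beyond the course. For renal dysfunction, Table 1 schedules creatinine at weeks 2, 6 and 10 in the intervention group only. Controls have none between screening and week 16, so a scheduled-test comparison within weeks 0-12 is not available.

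A phase-specific comparison has its own weakness. In weeks 0-12, Table 1 gives controls clinic visits at weeks 0, 6 and 12 and no calls. The intervention group has a visit or call about twice a week to week 6 and weekly thereafter. After week 12 the contact schedules are the same. Reported hypoglycemia will therefore be more complete in the intervention group in exactly the window of interest. This stands, and must be stated with the result.

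Finally, secondary outcomes are declared hypothesis-generating, and the investigators review safety monthly and more formally after 50 completers. Those reviews are oversight. They do not define what will be reported.

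**Conclusion.** The point holds as a cheap improvement. The plan specifies hypoglycemia rates only over a window of which 81% falls after the tested course, and it prespecifies no rate for the course itself. If rates after week 12 are equal between arms, the 64-week excess rate per person-year is 5.3 times smaller than the induction excess (about 5.0 with the taper).

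Two stronger readings are not supported. The first takes 5.3 as the factor by which relative risk is diluted. It applies to the excess rate only; depending on what happens after week 12, the ratio may not change at all. The second is that the 64-week window by itself makes a harmful course look neutral. That needs fewer intervention than control events after week 12. Since drugs stop at week 12 in eligible participants of both groups, a control rate that stays constant cannot be taken for granted. Under the assumed rates, the 64-week ratio is 0.90, 1.23 or 1.95 according to the control rate alone. Offsetting is plausible if controls relapse more often, but the documents give neither hypoglycemia rates nor drug exposure after week 12 from which to size it.

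**What to change.** In section 2.3, secondary question 5 and section 11.2, prespecify hypoglycemia rates by group, with person-time denominators, for:
- weeks 0-12, through the end of the insulin taper;
- the period thereafter;
- the full 64 weeks, reported alongside and not replaced.

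Show the proportion of each group on any glucose-lowering drug in each period. Do the same for genitourinary infection and ketoacidosis. Do not require it for cancers, fractures, deaths or renal dysfunction. State with the weeks 0-12 comparison that contact was much less frequent in controls.

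The cost is a few sentences and some table columns. The diary, the questioning at every contact and the week 12 visit in both groups should allow the split. The documents do not say that each event's onset date is recorded, so the case report form should be checked for this. The statistical price is fewer events and wider intervals per window: about 17.5 person-years per arm in weeks 0-12, against 93.5 over 64 weeks.

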## **3. STUDY PLAN AND PROCEDURES**

### **3.1 Overall study design and flow chart**

This is a randomized, open-label, 2-arm pilot trial in 152 patients with early T2DM. Participants will be randomly assigned to (i) an intensive metabolic intervention of 12 weeks in duration, or (ii) standard diabetes therapy, and followed for 64 weeks. In the intervention group, the intensive metabolic intervention will combine lifestyle therapy and intensive treatment with Forxiga, metformin and insulin glargine. Glucose-lowering medications will then be discontinued in all participants with a HbA1C < 7.3% on therapy, and participants will be encouraged to continue with lifestyle modification and regular home glucose monitoring. Participants with HbA1C  $\geq$  7.3% on therapy during week 12 of the trial or those with HbA1C  $\geq$  7.0% at or after the 24-week visit will receive standard glycemic management as informed by the 2013 Canadian Diabetes Association clinical practice guidelines. The visit schedule for study participants is shown in Table 1 in Appendix A.

## **4. SUBJECT SELECTION CRITERIA**

The Remission Evaluation of a Metabolic Intervention in Type 2 Diabetes with Forxiga trial will be conducted in participants with the following inclusion and exclusion criteria:

### **4.1 Inclusion criteria**

- 1) men and women 30-80 years of age inclusive;
- 2) type 2 diabetes mellitus diagnosed by a physician within 8 years prior to patient enrollment;
- 3) anti-diabetic drug regimen (either drug or dose of drug) unchanged during 8 weeks prior to screening and randomization;
- 4) HbA1C 6.5-9.5% inclusive on no hypoglycemic agents or HbA1C  $\leq$  8.0% on up to 2 glucose-lowering agents;
- 5) body mass index  $\geq$  23 kg/m^2;
- 6) ability and willingness to perform self-monitoring of capillary blood glucose (SMBG);
- 7) ability and willingness to self-inject insulin;
- 8) provision of informed consent.

## 4.2 Exclusion criteria

- 1) current use of insulin therapy;
- 2) history of hypoglycemia unawareness, or severe hypoglycemia requiring assistance;
- 3) history of end-stage renal disease or renal dysfunction as evidenced by eGFR < 60 mL/min/1.73 m^2 by MDRD formula;
- 4) history of lactic acidosis or diabetic ketoacidosis;
- 5) active liver disease or elevated alanine transferase (ALT) levels  $\geq 2.5$  times upper limit of normal at the time of enrollment;
- 6) history of bladder cancer or undiagnosed hematuria;
- 7) history of breast cancer;
- 8) history of polycythemia;
- 9) evidence of volume depletion or hypotension (systolic blood pressure < 90 mmHg);
- 10) systolic blood pressure > 180 mmHg or diastolic blood pressure > 105 mmHg;
- 11) diagnosed cardiovascular disease (unless cleared for a moderate intensity exercise program by a specialist) including:
  - a. any history of acute coronary syndrome, hospitalization for unstable angina, myocardial infarction, or revascularization with coronary artery bypass grafting or percutaneous coronary intervention;
  - b. other evidence of coronary artery disease;
  - c. peripheral vascular disease, valvular heart disease, cardiomyopathy, aortic dissection, tachyarrhythmias, bradyarrhythmias, prior stroke or TIA;
  - d. prior hospitalization for heart failure; or
  - e. ECG findings concerning for ischemic heart disease (i.e. pathological Q-waves, ST-segment-T-wave abnormalities in contiguous leads, left anterior hemiblock, left bundle branch block, second or third degree atrioventricular block).
- 12) dependence on oxygen;
- 13) history of any disease requiring frequent intermittent or continuous systemic glucocorticoid treatment;
- 14) history of bariatric surgery, or planned bariatric surgery in the next 1.5 years;
- 15) history of any major illness with a life expectancy of < 3 years;
- 16) history of injury or any other condition that significantly limits participant's ability to achieve moderate levels of physical activity;
- 17) any history of excessive alcohol intake, acute or chronic;
- 18) currently pregnant, or breastfeeding, or not using a reliable method of birth control for the duration of the trial in all females with childbearing potential; reliable methods of birth control include oral contraceptive (birth control pill), hormonal injection, implant, patch, or vaginal ring, intrauterine device, barrier method (condom and spermicide), tubal ligation, partner vasectomy or abstinence;
- 19) known hypersensitivity to Forxiga, metformin, or insulin glargine.

## **5. STUDY CONDUCT**

### **5.1 Screening and baseline evaluation**

At the screening assessment, informed consent will be obtained, and eligibility criteria will be assessed by performing an interview and physical examination. Blood will be drawn for creatinine, ALT, fasting plasma glucose (FPG), and HbA1C. Fasting serum samples will also be taken for storage at the screening visit in participants who agree to it. A urine pregnancy test (urine BhCG) will be performed in women with childbearing potential. A baseline electrocardiogram (ECG) will also be performed to assess for any evidence of ischemic heart disease or arrhythmia. Baseline weight, height, body mass index, waist circumference and hip circumference will be obtained in all study participants. Physical activity and food frequency questionnaires will also be administered at baseline.

### **5.2 Randomization and blinding**

#### **5.2.1 Procedures for randomization**

Eligible participants will be randomized 1:1 to (i) an intensive metabolic intervention of 12 weeks in duration, or (ii) standard diabetes therapy. An independent statistician will prepare a randomization schedule for each site using a computer-generated random number sequence. Concealment of allocation will be ensured by carrying out study group allocation through a central online system. In view of the differences in the treatment regimens, duration, and glycemic goals in the treatment groups, it will not be possible to blind participants or research staff to the intervention. However, the primary and key secondary outcomes of the study are based on objective measurements of blood glucose and HbA1C level, and lab personnel will be blinded to the treatment group assignment.

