### **5.4.3 Losses to follow-up**

Losses to follow-up are expected to be minimal as the study duration is only 64 weeks. The investigators will make every effort to contact participants who are lost to follow-up. In order to minimize losses to follow-up, participants who do not adhere to the assigned treatment or visit schedule will be encouraged to do HbA1C measurements through their regular diabetes care provider and will be contacted by telephone to collect key data. Participants who withdraw consent will be asked to return any study drugs to the study centre and encouraged to return to their regular diabetes care provider for assessment and further care.

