### **6.2 Study outcomes**

#### **6.2.1 Primary and secondary outcomes**

The primary outcome is drug-free diabetes remission, defined as a HbA1C < 6.5% without use of glucose-lowering agents for at least 12 weeks. Related outcomes to be analyzed include complete diabetes remission, defined as a HbA1C < 6.0% without use of glucose-lowering agents for at least 12 weeks, and diabetes regression, defined as a HbA1C of 6.5-6.9% without use of glucose-lowering agents for at least 12 weeks.

HbA1C will be measured in the local labs at 12, 24, 36, 48 and 64 weeks after randomization, during which use of glucose-lowering medications will also be ascertained. FPG will also be measured in the local lab at 16 weeks. All FPG levels will be measured approximately 48 hours after the last dose of any glucose-lowering medication unless fasting capillary glucose rises above 12 mmol/L.

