### **11.2 Statistical analyses**

All group comparisons will be conducted according to the intention-to-treat principle with inclusion of data from all participants according to their treatment group assignment, regardless of adherence to therapy. The primary outcome in this study is the proportion of patients in the intervention group who achieve drug-free diabetes remission 24 weeks after randomization compared to the control group. The treatment groups will be compared using a chi-squared test with  $\alpha = 0.05$  level of significance. The outcome will be reported as a risk difference in the induction of remission between the intervention group and the control group with 95% confidence interval. Any individual who withdraws/drops out prior to the 24, 36, 48 and 64 week visit will be classified as not having achieved drug-free diabetes remission at that point in time. Participants who fail to achieve remission or have hyperglycemia relapse will be censored with respect to diabetes remission outcomes.

For secondary analyses, a chi-squared test will be used for dichotomous outcomes and a two-sample t-test (or a non-parametric equivalent) for continuous outcomes. Secondary outcomes will be used only for generation of new hypotheses. Clinical and metabolic predictors of the successful induction of diabetes remission will be evaluated using logistic regression modeling. We do not plan to perform any interim analyses in this trial.

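### Randomisation is by site, but the primary chi-squared test and risk difference ignore site: a small efficiency loss whose size depends on an unstated blocking rule

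*Combined protocol and SAP*

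**What the plan says.** Section 5.2.1 of the combined protocol and SAP allocates participants 1:1 and states: "An independent statistician will prepare a randomization schedule for each site using a computer-generated random number sequence". It gives no block size or other rule for balancing the arms within a site. Section 5.4.1 plans 152 participants at about 7 sites and allows more sites if recruitment lags.

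Section 6.2.1 states: "HbA1C will be measured in the local labs at 12, 24, 36, 48 and 64 weeks after randomization". The primary outcome is remission, "defined as a HbA1C < 6.5% without use of glucose-lowering agents for at least 12 weeks". No central assay is described, although section 5.2.1 keeps lab personnel blinded to arm.

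For the primary analysis, section 11.2 states: "The treatment groups will be compared using a chi-squared test". The level is 0.05, and the effect is reported as a risk difference with a 95% confidence interval. Site appears in neither the test nor the estimate.

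Under section 5.4.3, participants who do not keep to treatment or visits "will be encouraged to do HbA1C measurements through their regular diabetes care provider", so some values may come from a lab other than the site's.

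**The concern.** The usual rule is to analyse as randomised: a factor that stratifies allocation belongs in the primary analysis if it may predict outcome. Here it plausibly does. A lab that reads slightly high or low moves people across a fixed threshold. It does so at week 24 against 6.5%, and also at week 12, when section 5.3.3 uses a cut-off of 7.3% to decide who stops drugs.

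If site predicts outcome and the arms are balanced within site, the pooled test charges between-site variation to error although the design has already removed it. Its type I error then falls below 5% and its interval is a little too wide. A site adjustment or pooling rule chosen after the data are seen would be open to challenge, so the choice should be made now.

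**Working it through.** **Inputs.** From the plan: 76 per arm, control remission 10%, differences of 20 and 23 points, alpha 0.05 (11.1, 11.2), and about 7 sites (5.4.1), which is 152/7, or about 22 per site. Assumed, because the documents give no figure: site effects normal on the log-odds scale, with SD from 0 to 1.0. SD 0.5 corresponds to site remission of roughly 20% to 40% (plus or minus 1 SD) around a mean of 30%; SD 1.0 corresponds to roughly 12% to 50%.

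**1. The plan's own figure.** Power = Phi[(d√n − 1.96√(2p̄(1−p̄))) / √(p1(1−p1)+p2(1−p2))]. For 10% vs 30% and n = 76: (0.2 × 8.718 − 1.96 × 0.5657)/0.5477 = 0.635/0.5477 = 1.159, which gives 87.7%. With continuity correction power is 82.9%. The stated 80% is therefore met with room to spare. For 10% vs 33% the same formulae give 94.0% and 91.1%, against a stated 90%.

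**2. How large a site effect could the assay produce?** Assume 30% are truly below 6.5%, week-24 HbA1C has SD 0.9, and a lab is offset by 0.2 points. The observed share is Phi(−0.524 ± 0.2/0.9), or about 23% or 38%. On the log-odds scale that is about ±0.37. With HbA1C SD 0.7 the shares are 21% and 41%; with SD 1.1 they are 24% and 37%. The log-odds shift then ranges from about 0.30 to 0.48. An offset of this size at every site gives a site SD below 0.5.

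**3. Why balance matters.** The pooled variance uses p̄(1−p̄), which equals the mean of p_k(1−p_k) over sites plus Var(p_k). With arms balanced within site, only the first part is real error. At p̄ = 0.20 and SD 0.5, Var(p_k) is about (0.5 × 0.16)² = 0.0064. Times 6/7 for seven sites this is 0.0055, or 3.4% of 0.16. The true standard error is √0.966 = 0.983 of the one used. Type I error is then 2[1 − Phi(1.96/0.983)], about 4.6%, and the interval is about 2% too wide. With unblocked schedules Var(p_k) is real error and the pooled variance is right.

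**4. Simulation.** Seven near-equal sites, marginal rates held at the values shown, no continuity correction. Rows with SD above 0 use 100,000 trials per cell, and blocked means permuted blocks of 4. Of the SD 0 rows, the blocked one uses exact balance (10,000 trials) and the unblocked one 60,000 trials.

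| Schedule | Site SD | Type I at 20%/20%: pooled / CMH | Power at 10%/30%: pooled / CMH |
|---|---|---|---|
| Blocked | 0 | 5.2% / 5.1% | 88.9% / 88.6% |
| Blocked | 0.25 | 4.9% / 4.9% | 88.8% / 88.7% |
| Blocked | 0.5 | 4.7% / 5.0% | 88.9% / 89.3% |
| Blocked | 1.0 | 3.8% / 4.9% | 89.1% / 90.9% |
| Unblocked | 0 | about 5% for the pooled test | 88.8% / 87.3% |
| Unblocked | 0.25 | 5.2% / 5.0% | 88.9% / 87.5% |
| Unblocked | 0.5 | 5.1% / 5.0% | 88.5% / 87.9% |
| Unblocked | 1.0 | 5.0% / 4.9% | 88.0% / 89.8% |

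A separate set of 60,000 trials per setting, with arms balanced within site, gave pooled type I error of 4.7% and 3.7% and CMH gains of 0.3 and 1.6 points at SD 0.5 and 1.0. The two sets agree to within about 0.2 points.

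**5. What unblocked schedules cost CMH.** With simple randomisation in K sites, the expected information kept is about (N − K)/(N − 1). For 7 sites this is 145/151 = 96%, in line with the loss of about 1.5 points at SD 0. For 14 sites it is 138/151 = 91%, and at SD 0.25 the simulated power is 88.9% pooled against 85.8% CMH.

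**The case against.** Most of the case against stands as a limit on size.

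- A reader might infer that site differences are known. The documents report none, in assay or in delivery. They are only plausible, and every site SD above is an assumption.
- A reader might infer that the pooled test is conservative as planned. That needs arms balanced within site, and section 5.2.1 states no blocking. With simple per-site sequences the pooled type I error is 4.8% to 5.2% at every SD examined.
- A reader might call stratification free. It is nearly so only if schedules are blocked.
- The assay argument alone does not reach the larger SDs. At SD 0.36 with exact balance, type I error is 4.9% pooled and 5.0% CMH, and power is 89.2% for both.
- A reader might count differences in how sites deliver treatment as a further shared site effect. Under sections 5.3.1 and 5.3.2, site staff guide titration and lifestyle work in the intervention arm, while the regular provider manages glucose in controls. With site effects in the intervention arm only and exact balance, pooled and CMH power are 86.5% and 86.3% at SD 0.5, and 81.1% and 81.5% at SD 1.0. Stratifying recovers almost nothing there.
- A reader might infer that local labs bias the comparison. A lab's offset applies to both arms at its site, so it creates no false treatment effect. The use of another provider's lab in section 5.4.3 is a way to limit missing data, and the documents give no basis for putting a number on its effect.

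What these points leave untouched is that the analysis does not follow the randomisation, and that the rule deciding whether this matters is not written down.

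**Conclusion.** The point holds as a small matter of efficiency and prespecification. It does not threaten validity: there is no bias and no inflation of type I error. With seven sites, arms balanced within site and a shared site effect of SD 0.5 to 1.0, the pooled test runs at about 4.7% down to 3.7%, and CMH gains about 0.3 to 1.6 points of power. With unblocked schedules the pooled test holds 5%, and switching to CMH changes power by about −1.6 points (no site effect) to +1.8 points (SD 1.0). In every setting run, including site effects confined to one arm, pooled power stays above the stated 80%, so the sample size need not change. The direction of the gain rests on the blocking rule and its size on the assumed site SD. The documents supply neither.

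**What to change.** - **Section 11.2:** make the primary test a CMH test stratified by randomising site, and report the Mantel-Haenszel risk difference with its 95% confidence interval. Say in advance how very small or late-added sites are pooled. Keep the unstratified test and risk difference as supportive.
- **Section 5.2.1:** use permuted blocks within site and say so. Because the trial is open-label, vary the block size and do not disclose it to sites. If schedules already exist, state the rule they used.
- **Optional, sections 6.2.1 and 5.4.3:** record which lab produced each HbA1C value.

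The cost is a few sentences of text, a pooling rule and, if wanted, one data field. If sites do not differ, the price in power with seven sites is about 0.3 points when blocked and up to about 1.6 points when unblocked. With 14 unblocked sites and a small site effect (SD 0.25) it is about 3 points (88.9% to 85.8%), which is why the blocking rule and the pooling rule should come with the change. If the sponsor prefers to keep the pooled test as primary, prespecifying the stratified analysis as a sensitivity analysis would settle most of the point.
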